9 STATISTICAL ANALYSIS PLAN

9.1 Statistical Analysis Plan Summary

The analysis for the primary endpoint will be on the natural log scale of the AHI data. Natural log-transformed fold change from baseline values for AHI will be analyzed using a linear mixed effects model. The dependent variable is natural log (treatment/baseline), and the independent variables in the model include terms for treatment, sequence, and period. In addition, the between-treatment difference in baseline AHIs ($X_{diff_AB} = \ln(\text{baseline of MK-7264}/\text{baseline of Placebo})$) will be used as a covariate in the model, along with a treatment by X_{diff_AB} interaction; the latter term allows for the fact that the correlation between change from baseline and baseline may differ by treatment. An unstructured covariance matrix will be used to allow for unequal treatment variances and to model the correlation between treatment measurements within each subject via the REPEATED statement in SAS PROC MIXED. Least square means and 95% confidence intervals will be calculated for each treatment. These least square means and 95% CIs will be exponentiated to obtain the geometric mean fold change from baseline for each treatment. The least square mean treatment differences (MK-7264 - Placebo) and corresponding 90% CIs in natural log transformed change from baseline will be calculated from the model. The treatment differences and CIs will be exponentiated to obtain the geometric mean treatment fold differences (MK-7264/placebo) and corresponding CIs. If the upper limit of this 90% CI is less than 1.00, then it will be concluded that the administration of MK-7264 has statistically significantly lowered the AHI, thus satisfying the primary hypothesis.

9.2 Responsibility for Analyses

The statistical analysis of the data obtained from this study will be conducted by, or under the direct auspices of, the Early Clinical Development Statistics Department in collaboration with the Quantitative Pharmacology and Pharmacometrics Department and Translational Pharmacology Department of the Sponsor.

If, after the study has begun, changes are made to the statistical analysis plan stated below, then these deviations to the plan will be listed, along with an explanation as to why they occurred, in the Clinical Study Report.

9.3 Hypotheses/Estimation

Primary:

Hypothesis: Multiple dose administration of MK-7264 in participants with moderate to severe OSA reduces the AHI relative to placebo. A 30% reduction in AHI as compared to placebo is expected.

Secondary:

Objective: To evaluate the safety and tolerability of MK-7264 following multiple dose administration of MK-7264.

Exploratory Objectives:

- To evaluate the pharmacokinetics of MK-7264 in participants with moderate to severe OSA.
- To evaluate arousal index following multiple dose administration of MK-7264 in participants with moderate to severe OSA.
- To evaluate the proportion of stage N1 non-REM sleep following multiple dose administration of MK-7264 in participants with moderate to severe OSA.
- To estimate mean SaO₂ during total sleep time (TST), NREM, REM, and awake time following the administration of multiple doses of MK-7264 in participants with moderate to severe OSA.
- To evaluate the proportion of the night during TST and sleep stages in which SaO₂ is less than 90% following multiple dose administration of MK-7264 in participants with moderate to severe OSA
- To evaluate loop gain following multiple dose administration of MK-7264 in participants with moderate to severe OSA.
- To evaluate morning systolic and diastolic blood pressure following multiple dose administration of MK-7264 in participants with moderate to severe OSA.
- To evaluate daytime sleepiness following multiple dose administration of MK-7264 in participants with moderate to severe OSA.
- To evaluate the performance of the Emerald Device to capture sleep data
- To evaluate blood and urine biomarkers

- To explore the relationship between genetic variation and response to the treatment(s) administered, and mechanisms of disease. Variation across the human genome may be analyzed for association with clinical data collected in this study

9.4 Analysis Endpoints

Primary:

AHI, which is sum of the apnea and hypopnea indices, is the primary outcome measure. The apnea index for each participant will be calculated as the number of apneas divided by the total sleep time. The hypopnea index for each participant is calculated as the number of hypopneas divided by the total sleep time. The AHI will be calculated as the number of apneas and hypopneas divided by the total sleep time. Baseline AHI for each period are obtained on Day-1. Individual AHI fold-change from baseline in each treatment period will be calculated as the ratio (on-treatment AHI/baseline AHI).

Secondary:

Adverse experiences and other safety measurements (e.g., vital signs, ECGs, laboratories)

Exploratory Endpoints:

- MK-7264 (plasma PK): C_{max}, AUC₀₋₂₄, CL, and t_{1/2}
- Arousal Index for TST, REM, and NREM
- Mean SaO₂ for TST, REM, NREM, and Awake time. Baseline mean SaO₂ for each period is obtained on Day-1. Individual mean SaO₂ fold-change from baseline in each treatment period will be calculated as the ratio (on-treatment mean SaO₂/baseline mean SaO₂).
- Proportion of the night during TST, REM, NREM, and Awake time in which SaO₂ <90%.
- Proportion of stage N1 non-REM to TST
- Loop Gain at various sleep stages
- Change in Systolic and Diastolic blood pressure (BP at Lights on – BP at -1.5 hr)
- ESS, Morning Sleep Questionnaire (MSQ), and FOSQ scores
- Emerald Device sleep data (Not in the scope of the current analysis plan. A separate statistical analysis plan will be drafted, and a separate memo will be prepared)

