As of 31-AUG-2018, MK-7264 has been administered to 360 study subjects in 12 completed and 2 ongoing (clinically complete) Phase 1 clinical trials. Single oral doses, 10 to 1800 mg, and multiple oral doses, 7.5 mg to 1800 mg BID for up to 14 days, were administered to healthy subjects. The efficacy of MK-7264 has been investigated in 11 completed Phase 2 clinical trials. Eight of these trials included subjects with chronic cough; 2 studies were conducted in subjects with idiopathic pulmonary fibrosis (IPF) related cough. Efficacy of MK-7264 was also evaluated in other indications, such as osteoarthritis pain, interstitial cystitis/bladder pain syndrome, and asthma. Across studies, MK-7264 was well tolerated, the most common AEs being dose-dependent effects on taste sensation - eg, dysgeusia, ageusia, hypogeusia. Subjects also described oral paresthesia (tingling sensation in the mouth and/or throat) and oral hypoesthesia (numbness/reduced sensitivity often limited to a specific place in mouth, eg, side of the tongue, lip, back of throat). The taste disturbances and oral paresthesia/hypoesthesia were fully and rapidly reversible after discontinuation of the drug.

Pharmacokinetics of MK-7264 has been evaluated in a wide dose range from 7.5 mg to 1800 mg. MK-7264 is rapidly absorbed, with a median T_{max} of 1.0 to 2.0 hours, and has a half-life of approximately 7 to 10 hours. The exposure to MK-7264 increases in proportion to the dose until 450 mg and it increase in a less than dose proportional manner beyond it. Steady state appears to be achieved within 2 to 3 days of BID dosing, with accumulation ratio of approximately 1.2- to 1.4 fold in the clinical dose range. However, with once daily administration the accumulation is expected to be minimal. Elimination of MK-7264 occurs primarily via renal excretion of intact MK-7264 as approximately 64% of the MK-7264 dose was recovered as parent drug in urine. Metabolism is a relatively minor pathway of elimination, with approximately 15% of an oral dose appearing in urine and feces as metabolites in healthy adult male subjects. The exposure of MK-7264 is inversely related to renal function. Based on linear regression analyses between eGFR and PK parameters, AUC was predicted to be 2.74 and 3.68 times higher and C_{max} 1.70 and 1.99 times higher in subjects with moderate and severe impairment, respectively, compared with healthy subjects with normal renal function.

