| 
 To evaluate the proportion of the night during TST and sleep stages in which SaO₂ is less than 90% following multiple dose administration of MK-7264 in participants with moderate to severe OSA | 
 Proportion of the night during TST and sleep stages in which SaO₂ is less than 90% |
| 
 To evaluate loop gain following multiple dose administration of MK-7264 in participants with moderate to severe OSA. | 
 Loop gain |
| 
 To evaluate morning systolic and diastolic blood pressure following multiple dose administration of MK-7264 in participants with moderate to severe OSA. | 
 Morning systolic and diastolic blood pressure |
| 
 To evaluate daytime sleepiness following multiple dose administration of MK-7264 in participants with moderate to severe OSA. | 
 Morning Sleep Questionnaire Epworth Sleepiness Scale (ESS) score (0-24), units on a scale. Functional Outcomes of Sleep Questionnaire (5-20). |
| 
 To evaluate the performance of the Emerald Device to capture sleep data | 
 Emerald Device sleep data |
| 
 To evaluate blood and urine biomarkers | 
 Exploratory biomarkers |
| 
 To explore the relationship between genetic variation and response to the treatment(s) administered, and mechanisms of disease. Variation across the human genome may be analyzed for association with clinical data collected in this study | 
 Germline genetic variation |

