4 STUDY DESIGN

4.1 Overall Design

This is a randomized, placebo-controlled, crossover, double-blind multi-site study of MK-7264 in participants with OSA.

The majority of study assessments and procedures for each participant will be conducted during the 6 overnight clinic visits. Eligible participants from Screening 1 will be asked to arrive at the clinic on Day -22 for Screening 2. The participants will have a PSG recording during Screening 2 where their diagnosis of OSA is confirmed.

The participants with confirmed OSA from Screening 2 will be asked to return to the clinic on Day -15 for Screening 3. During Screening 3, the participants will undergo a second PSG with supplemental inspired oxygen to assess whether their sleep apnea is “chemoreflex dependent”. While asleep during the PSG, supplemental oxygen will be delivered via face mask (40% inspired oxygen) as an addition to the standard sleep study [Narkiewicz, K., et al 2016] [Sands, S. A., et al 2018]. In some participants the addition of supplemental oxygen will decrease carotid body hyperreflexia thereby lowering loop gain and leading to reduced AHI in those with “chemoreflex dependent” OSA. The number of AHI episodes, as verified by a central reader will be determined. If the participant has a ≥ 30 percent decrease in AHI events as well as airflow-based hypopnea events (>30% reduction in airflow) that do not meet normal criteria (3% desaturation or arousal) compared to Screening 2 (see Operations Manual for details), he/she will be eligible to be randomized into the study and may return to the clinic on Day -1 for Period 1 of the study.

During Periods 1 and 2 participants will have a baseline PSG and will receive study intervention for at-home dosing. Participants will begin self-administering study drug at-home (in the evening) for 6-days. Participants will return to the clinic on Day 7 for the last day study drug administration and an assessment PSG. Study drug will be discontinued for a 7-day washout at home before the second period.

Following completion of Period 2, participants will return to the clinic 14 days following the last study drug administration for a follow-up visit.

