8.12.5 Critical Procedures Based on Study Objectives: Timing of Procedure

For this study, the PSG is the critical procedure.

At any postdose time point, the PSG needs to be started as close to the exact start time relative to dosing as possible. All other procedures should be performed as close to the prescribed/scheduled time as possible. Study procedures can be performed prior or after the prescribed/scheduled time.

The order of priority can be changed during the study with joint agreement of the investigator and the Sponsor Clinical Director.

Any nonscheduled procedures required for urgent evaluation of safety concerns take precedence over all routine scheduled procedures.

The following variance in procedure collection times will be permitted.

- PSG Lights-Off Time for Baseline and Assessment Visits (+/- 1 hour)
- Predose PK Collection: - 60 minutes from scheduled time within PSG day
- Postdose PK Collection: + 60 minutes from scheduled time within PSG day
- Laboratory Safety Tests: +120 minutes from scheduled time within PSG day
- Predose Vital Signs: - 60 minutes from scheduled time within PSG day
- Postdose Vital Signs: +120 minutes from scheduled time within PSG day

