The posterior probability that the true mean percent reduction in AHI after multiple doses of MK-7264 compared to placebo exceeds 10, 20, 30, 40 and 50% will also be obtained, assuming normality and a non-informative prior.

Secondary Endpoints

Safety and tolerability will be evaluated following multiple doses of MK-7264 administered to the participants with OSA by clinical assessment of adverse experiences and other safety measurements (vital signs, ECGs, laboratories). Summary statistics will be provided as appropriate.

Exploratory Endpoints

Population pharmacokinetics approach will be utilized for evaluating MK-7264 plasma PK parameters, C_{max}, AUC₀₋₂₄, CL, and t_{1/2}. The population PK results will be presented in a separate memo.

Mean SaO₂: The analysis for the mean SaO₂ will be on the natural log scale. Natural log-transformed fold change from baseline values for mean SaO₂ will be analyzed using the above described model. Baseline is defined as the mean SaO₂ during total sleep time on day-1 for each period. The mean SaO₂ during REM, NREM and Awake time will be analyzed in a similar fashion.

Proportion of the Night SaO₂ <90%: Summary statistics will be provided for the percentage of participants who experience a SaO₂ level less than 90% during the TST by treatment. Summary statistics will also be provided for the proportion of the night during total sleep time in which SaO₂ is <90% by treatment. The proportion of the night SaO₂<90% during various sleep stages, REM, NREM, and Awake time will also be summarized.

Descriptive summary statistics will be provided for the following exploratory endpoints including arousal index, loop gain at various sleep stages, and proportion of stage N1 NREM to TST. Some of these parameters may also be analyzed in models as previously described to explore the effect of MK-7264 on these parameters.

To assess the day time sleepiness and quality of life improvement, descriptive statistics will be provided for ESS, MSQ, and FOSQ scores. The relationship between the AHI and loop gain at different sleep stages and the relationship of AHI and various scores (ESS, MSQ, and FOSQ) will be explored graphically.

To explore the effect of MK-7264 on diastolic (DBP) and systolic blood pressure (SBP), the difference (BP at Lights on – BP at -1.5 hr) will be computed on the original scale. Summary statistics for this difference in the BP for both diastolic and systolic blood pressure readings will be computed.

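### The objective is morning blood pressure, but the SAP analyses lights-on minus evening pressure, which removes any drug effect the two readings share

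*Combined protocol and SAP*

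**What the plan says.** Section 3 states the objective as "To evaluate morning systolic and diastolic blood pressure following multiple dose administration of MK-7264 in participants with moderate to severe OSA" and lists morning pressure itself as the endpoint, with nothing subtracted. SAP 9.3 repeats the objective: "To evaluate morning systolic and diastolic blood pressure following multiple dose administration of MK-7264". The rationale in 4.2.1.1 is that lower sympathetic drive might help normalise blood pressure; it does not describe an effect confined to the night.

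SAP 9.4 defines a different quantity, "Change in Systolic and Diastolic blood pressure (BP at Lights on – BP at -1.5 hr", and 9.6 confirms that "the difference (BP at Lights on – BP at -1.5 hr) will be computed on the original scale", followed by summary statistics for that difference. Neither section names the night.

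The detailed schedule for PSG days in 1.3 puts vital signs at -1.5 h and at lights-on (8 h), and puts assessment-night dosing at -1.5 h too. Section 8.12.5 gives timing allowances for both readings: "Predose Vital Signs: - 60 minutes from scheduled time within PSG day" and "Postdose Vital Signs: +120 minutes from scheduled time within PSG day". Section 4.1 describes the doses taken before the assessment visit: "Participants will begin self-administering study drug at-home (in the evening) for 6-days".

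**The concern.** The objective asks what the drug does to morning pressure. The planned endpoint estimates the morning effect minus the evening effect. An evening reading can serve as a baseline only if it is free of drug, and on the assessment night it comes after six doses. A drug that lowered (or raised) pressure round the clock could therefore show no change in the only summary assigned to this objective, and a reader could wrongly conclude that morning pressure was unaffected.

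The stakes are limited. No test, decision rule or sample-size claim rests on this endpoint.

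**Working it through.** The plan gives no blood-pressure effect size, variability or power, so it has no figure to reproduce. The check is algebra, followed by an illustration of size.

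**1. What the planned contrast estimates.** Let the placebo means be M at lights-on and E at -1.5 h. On drug they are M + d and E + r·d, where r is the evening effect as a share of the morning effect.

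- Planned: [(M + d) − (E + r·d)] − [M − E] = (1 − r)d.
- Lights-on only: (M + d) − M = d.

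The two agree only if r = 0. Subtracting the Day -1 overnight difference as well does not help: Day -1 carries no drug effect in either period, so the term r·d from the assessment night stays subtracted.

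**2. Is r likely to be 0?** Inputs from the documents:

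- Dose at about -1.5 h and lights-on at 8 h (1.3, 8.1.8.1), so lights-on is 9.5 h after the dose.
- The evening reading is predose, about 24 h after the sixth home dose.
- The drug "has a half-life of approximately 7 to 10 hours" (2.4).

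The ratio of evening to lights-on concentration is 2^(−(24 − 9.5)/half-life) = 2^(−14.5/half-life). This is 0.238 at 7 h, 0.307 at 8.5 h (the midpoint) and 0.366 at 10 h. Adding up all doses (six before the evening reading, seven before lights-on) gives the same 0.238 and 0.366. The evening level is thus about 24% to 37% of the lights-on level.

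**3. Illustrative size.** Assume a true lowering of 6 mmHg at lights-on. The planned difference then shows 6 × (1 − effect ratio), in mmHg:

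| Assumption | 7 h | 8.5 h | 10 h |
|---|---|---|---|
| Effect proportional to concentration, nominal times | 4.57 | 4.16 | 3.80 |
| Proportional, limits of the vital-sign windows | 4.08 | 3.65 | 3.30 |
| Half-saturated at the lights-on level, nominal times | 3.69 | 3.18 | 2.78 |
| Equal effect at both readings | 0 | 0 | 0 |

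- Row 1: effect ratio = r from step 2, so 63% to 76% of the effect is kept.
- Row 2: the evening reading is 60 min early (23 h after a dose) and the lights-on reading 120 min late (11.5 h). Then r = 2^(−11.5/half-life) = 0.320, 0.391 and 0.451, and 55% to 68% is kept.
- Row 3: an Emax curve with EC50 equal to the lights-on concentration gives an effect ratio of 2r/(1 + r), with r from step 2.

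**4. Is a drug-free reading available?** Yes. Section 1.3 schedules vital signs at both Baseline and Assessment, and the PSG-day table places them at -1.5 h and lights-on. Day -1 of Period 1 precedes any dosing. Day -1 of Period 2 follows a 7-day washout: 168 h ÷ 10 h ≈ 17 half-lives, or 168 h ÷ 7 h = 24.

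**The case against.** The best defence is that the overnight change is a deliberate way of expressing morning pressure. It adjusts the lights-on reading for the same person's level a few hours earlier, which removes day-to-day drift, and it suits a bedtime dose meant to act at night. That is a reasonable descriptive quantity, but it answers a different question from the stated objective, and the SAP neither explains nor acknowledges the switch.

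Second, morning pressure is not lost: vital signs are summarised for safety and 9.6 promises individual listings by treatment, from which a paired comparison could be made. That is true of the data. But the safety summaries are promised only as appropriate, and neither they nor the listings commit to a treatment comparison of lights-on pressure.

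Third, the night is not named. If the -1.5 h reading were the Day -1 value, the cancellation would not arise. The same-night reading is the natural one, because 9.4 says Day -1 where it means the period baseline. This is still an inference, and the text needs correcting on either reading.

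Fourth, the millimetre figures rest on an assumed effect and assumed exposure-response shapes, and the window-limit row needs both readings at opposite extremes with the previous home dose exactly on time. This stands: the figures show a range of possible losses and do not estimate the actual one.

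**Conclusion.** The concern holds, as a minor point. The objective in Section 3 and SAP 9.3 and the endpoint in SAP 9.4 and 9.6 are different quantities. On the natural same-night reading, the planned contrast is (1 − r) times the morning effect. That result is exact; its size is not known. With the documents' half-life and an effect proportional to concentration, about a quarter to somewhat over a third of the effect would be lost at nominal times (24% to 37%). A sustained effect would vanish. Section 4.3 makes a substantial evening effect plausible: it expects daytime concentrations similar to those of 45 mg BID, a regimen it calls near-maximal for cough. Whether that carries over to blood pressure is unknown.

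The primary AHI conclusion is unaffected.

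**What to change.** In SAP 9.4 and 9.6:

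- Define the endpoint as lights-on systolic and diastolic pressure on the assessment night, summarised by treatment as change from the Day -1 lights-on reading of the same period. This follows the use of Day -1 as period baseline for AHI and mean SaO2.
- Report the MK-7264 minus placebo difference on the original scale. Using the existing crossover model is optional; descriptive statistics would meet the objective.
- Keep the lights-on minus -1.5 h difference as an additional description, and state which night it refers to.

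The cost is a change of SAP wording and one added summary. No new measurement or visit is needed.

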9.5 Analysis Populations

The following populations are defined for the analysis and reporting of data. All participants will be reported, and their data analyzed, according to the treatment(s) they actually received.

All Participants as Treated (ASaT): The All Participants as Treated Population consists of all participants who received at least one dose of treatment. This population will be used for assessments of safety and tolerability.

Per-Protocol (PP): The Per-Protocol Population consists of the set of data generated by the subset of participants who comply with the protocol sufficiently to ensure that these data will be likely to exhibit the effects of treatment, according to the underlying scientific model. Compliance covers such considerations as exposure to treatment, availability of measurements and absence of important protocol deviations. Important protocol deviations will be identified to the extent possible prior to unblinding by individuals responsible for data collection/compliance, and its analysis and interpretation. Any participants or data values excluded from analysis will be identified, along with their reason for exclusion, in the CSR. At the end of the study, all participants who are compliant with the study procedure as aforementioned and have available data from at least one treatment will be included in the Per-Protocol dataset. This population will be used for the PK and efficacy analyses.

